8.4 EXPLORATORY MEASURES

- Ocular itching evaluated by the subject at Visit 5b, 6a, 6b, and 7 at 15(± 1), 20(± 1), 25(± 1) and 30(± 1) minutes post-CAC (0-4 scale, allowing half-unit increments).
- Tearing evaluated by the subject at Visits 5b, 6a, 6b, and 7 at 25(± 1) and 30(± 1) minutes post-CAC (0-4 scale, NOT allowing half-unit increments)
- Eyelid swelling evaluated by the subject at Visits 5b, 6a, 6b, and 7 at 25(± 1) and 30(± 1) minutes post-CAC (0-3 scale, NOT allowing half-unit increments)
- Rhinorrhea, nasal pruritis, ear or palate pruritis, and nasal congestion evaluated by the subject at Visits 5b, 6a, 6b, and 7 at 25(± 1) and 30(± 1) minutes post-CAC (0-4 scale, NOT allowing half-unit increments)
- Conjunctival, episcleral, and ciliary redness evaluated by the investigator at Visit 5b, 6a, 6b, and 7 at 25(± 1) and 30(± 1) minutes post-CAC (0-4 scale, allowing half-unit increments).
- Chemosis evaluated by the investigator at Visit 5b, 6a, 6b, and 7 at 25(± 1) and 30(± 1) minutes post-CAC (0-4 scale, allowing half-unit increments).
- In a subset of approximately 36 subjects who agree to undergo confocal microscopy, Conjunctival Inflammation as measured by confocal microscopy (0-4 scale, NOT allowing half-unit increments) at Visits 3, 4b, and 7. This number is estimated to be sufficient to ensure approximately 30 subjects in the confocal microscopy subset complete the trial.

- In this same subset of subjects who undergo confocal microscopy, tears will be collected from both eyes (prior to confocal microscopy) at Visit 3, 4a, 4b and 7. At Visit 3, tears will be collected both pre- and post-CAC. At Visit 4a tears will be collected prior to dosing. Tears will be analyzed for cytokine levels.
- Diary assessments for subset of subjects undergoing confocal microscopy at Visits 3 and 4b. Additionally, all subjects will be dispensed diaries at Visits 5b and 6b. Assessments of ocular itching, ocular redness, and eyelid swelling will occur prior to bedtime and upon awakening (all use a 0 to 4 scale, except eyelid swelling, 0 to 3).
- Digital photographs will be taken at-home of each eye (for subset of subjects undergoing confocal microscopy) prior to subjects completing diary assessments following Visits 5b and 6b.
- Digital photographs will be taken in-office of all subjects pre-CAC and within 30 minutes of the last post-CAC assessment at Visit 4b and Visit 5a

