10.3.1.9 VISIT 6b (8 [+1] Hours post-Visit 6a,): 5th Dose/CAC #5

- Update of Medical/Medication History
- Adverse Event Query
- Visual Acuity Utilizing an ETDRS Chart: A clinically significant visual acuity decrease (defined as an increase of 0.22 or greater in logMAR score) from Visit 2 will be considered an adverse event.
- Pre-CAC Ocular and Nasal Allergic Signs and Symptoms Assessment
- Slit Lamp Biomicroscopy
- Investigational Product Instillation: [REDACTED]
[REDACTED]
[REDACTED]
- Conjunctival Allergen Challenge (CAC): [REDACTED]
[REDACTED]
[REDACTED]
- Post-CAC Ocular and Nasal Allergic Signs and Symptoms Assessment: Assessment of itching will be made by the subject at 5(±1), 7(±1), 10(±1), 15(±1), 20(±1), 25(±1), and 30(±1) minutes following allergen challenge. Assessments of redness and chemosis will be graded by the Investigator at 7(±1), 15(±1), 20(±1), 25(±1) and 30(±1) minutes post-challenge. Assessments of eyelid swelling, tearing/watery eyes, and nasal symptoms will be made by the subject at 7(±1), 15(±1), 20(±1), 25(±1), and 30(±1) minutes post-challenge (**Appendix 2**).

- *Diary Dispensation*: All subjects will be dispensed a diary to complete daily assessments prior to bedtime and upon awakening until the morning of Visit 7. Subjects will be instructed to bring the diary to the next visit (Visit 7) for a compliance check.
- *Ora Photography System*: The subset of subjects who underwent confocal microscopy will be dispensed cameras for at home assessments, to be done alongside diary assessments.
- *Adverse Event Query*
- *Scheduling of next visit (Visit 7)*: Subjects will be asked to return to the office the following day (Day 17) Visit 7.

10.3.1.10 Visit 7(24 hours (± 6 hrs) Post-Dose at Visit 6a): 6th Dose/CAC #6

- *Update of Medical/Medication History*
- *Adverse Event Query*
- *Assessments Diary Review and Collection*: Assessments diary will be collected and reviewed for compliance from Visit 6b to Visit 7 and to address any queries.
- *Urine Pregnancy Testing*: This will be given to all women of childbearing potential
- *Visual Acuity Utilizing an ETDRS Chart*: A clinically significant visual acuity decrease (defined as an increase of 0.22 or greater in logMAR score) from Visit 2 will be considered an adverse event.
- *Pre-CAC Ocular and Nasal Allergic Signs and Symptoms Assessment*
- *Slit Lamp Biomicroscopy*
- *Digital Imaging*: Digital photographs may be taken of each eye.
- *Investigational Product Instillation*: [REDACTED]

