[REDACTED]
[REDACTED]
[REDACTED]
- *Conjunctival Allergen Challenge (CAC)*: [REDACTED]
[REDACTED]
[REDACTED]
- *Post-CAC Ocular and Nasal Allergic Signs and Symptoms Assessment*: Assessment of itching will be made by the subject at 5(± 1), 7(± 1), 10(± 1), 15(± 1), 20(± 1), 25(± 1), and 30(± 1) minutes following allergen challenge. Assessments of redness and chemosis will be graded by the Investigator at 7(± 1), 15(± 1), 20(± 1), 25(± 1) and 30(± 1) minutes post-challenge. Assessments of eyelid swelling, tearing/watery eyes, and nasal symptoms will be made by the subject at 7(± 1), 15(± 1) and 20(± 1) minutes post-challenge (**Appendix 2**).

- Visual Acuity Utilizing an ETDRS Chart: A clinically significant visual acuity decrease (defined as an increase of 0.22 or greater in logMAR score) from Visit 2 will be considered an adverse event.
- Slit Lamp Biomicroscopy
- Digital Imaging: Digital photographs may be taken of each eye within 30 minutes of the last post-CAC assessment.
- Confocal Microscopy: Following digital photographs, the same subset of subjects that underwent confocal at Visit 3 will undergo confocal microscopy of the left eye.
- Tear Collection: Tears (5 μ L from each eye) will be collected from the confocal subset 2 hours (+1 hours) after instillation of the anesthetic used for confocal microscopy procedures. The technician collecting tears will note the subject's reflex tearing, if applicable (see **Appendix 2**).
- IOP Measurement: Intraocular Pressure (IOP) will be measured in each eye by contact tonometry.
- Dilated Ophthalmoscopy: A dilated ophthalmoscopy will be performed by the Investigator to evaluate the presence or absence of clinically significant fundus abnormalities and vitreous pathology.
- Relief Drop Instillation: Subjects may receive a dose of a currently marketed, topical ophthalmic anti-allergic agent (i.e., anti-histamine/vasoconstrictor combination products like Visine®-A®) as they leave the office to relieve any immediate discomfort caused by the allergic reaction.
- Adverse Event Query
- Study Exit

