2.5 Exploratory Measures

The exploratory measures include the following:

- Ocular itching evaluated by the subject at Visit 5b, 6a, 6b, and 7 at 15(± 1), 20(± 1), 25(± 1) and 30(± 1) minutes post-CAC (0-4 scale, allowing half-unit increments)
- Tearing evaluated by the subject at Visits 5b, 6a, 6b, and 7 at 25(± 1) and 30(± 1) minutes post-CAC (0-4 scale, NOT allowing half-unit increments)
- Eyelid swelling evaluated by the subject at Visits 5b, 6a, 6b, and 7 at 25(± 1) and 30(± 1) minutes post-CAC (0-3 scale, NOT allowing half-unit increments)

- Rhinorrhea, nasal pruritis, ear or palate pruritis, and nasal congestion evaluated by the subject at Visits 5b, 6a, 6b, and 7 at 25(± 1) and 30(± 1) minutes post-CAC (0-4 scale, NOT allowing half-unit increments).
- Conjunctival, episcleral, and ciliary redness evaluated by the investigator at Visit 5b, 6a, 6b, and 7 at 25(± 1) and 30(± 1) minutes post-CAC (0-4 scale, allowing half-unit increments).
- Chemosis evaluated by the investigator at Visit 5b, 6a, 6b, and 7 at 25(± 1) and 30(± 1) minutes post-CAC (0-4 scale, allowing half-unit increments).
- In a subset of approximately 36 subjects who agree to undergo confocal microscopy, conjunctival inflammation as measured by confocal microscopy (0-4 scale, NOT allowing half-unit increments) at Visits 3, 4b, and 7.
- In the same subset of subjects who undergo confocal microscopy, tears will be collected from both eyes (prior to confocal microscopy) at Visit 3, 4b, and 7. At Visit 3, tears will be collected at two separate time points post-CAC: prior to the confocal microscopy procedures and again at 2 (+1) hours after instillation of the anesthetic used for the confocal microscopy procedures. At Visit 4b tears will be collected prior to the confocal microscopy procedures post-CAC. At Visit 7 tears will be collected 2 (+1) hours after instillation of the anesthetic used for the confocal microscopy procedures post-CAC. Tears will be analyzed for cytokine levels.
- Diary assessments for the subset of subjects undergoing confocal microscopy at Visits 3 and 4b. Additionally, all subjects will be dispensed diaries at Visits 5b and 6b. Assessments of ocular itching, ocular redness, and eyelid swelling will occur prior to bedtime and upon awakening (all use a 0 to 4 scale, except eyelid swelling, 0 to 3).

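### The Visit 7 procedure stops the eyelid, tearing and nasal scores at 20 minutes, although the synopsis, protocol 8.4 and the SAP list them at 25 and 30 minutes at that visit

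*Protocol*

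**What the plan says.** Protocol 8.4 lists, among the exploratory measures, "Tearing evaluated by the subject at Visits 5b, 6a, 6b, and 7 at 25(± 1) and 30(± 1) minutes post-CAC" and "Eyelid swelling evaluated by the subject at Visits 5b, 6a, 6b, and 7 at 25(± 1) and 30(± 1) minutes post-CAC". It has a matching entry for rhinorrhea, nasal pruritus, ear or palate pruritus and nasal congestion. The synopsis repeats these entries, as do SAP 2.5 and SAP 16. SAP 16 says that the measures will be collected and that a selection of them will be listed and summarised.

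The procedures for Visits 5b, 6a and 6b (protocol 10.3.1.7 to 10.3.1.9) agree with those lists. The Visit 6b text, for example, says that "nasal symptoms will be made by the subject at 7(±1), 15(±1), 20(±1), 25(±1), and 30(±1) minutes post-challenge".

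The Visit 7 procedure (10.3.1.10) differs: "Assessments of eyelid swelling, tearing/watery eyes, and nasal symptoms will be made by the subject at 7(± 1), 15(± 1) and 20(± 1) minutes". The sentence just before it keeps the investigator's ratings going to 30 minutes: "Assessments of redness and chemosis will be graded by the Investigator at 7(± 1), 15(± 1), 20(± 1), 25(± 1) and 30(± 1) minutes post-challenge". Itching at Visit 7 is also scored to 30 minutes.

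On the diary, protocol 8.4 lists "Diary assessments for subset of subjects undergoing confocal microscopy at Visits 3 and 4b", and the synopsis and SAP 2.5 do the same. The Visit 3 procedure dispenses a diary to the confocal subset and the Visit 4a procedure collects it. The Visit 4b procedure has no diary step, and neither does the Visit 5a procedure.

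**The concern.** A score that is not taken at 25 or 30 minutes after the challenge cannot be recovered later. A site working from the visit-by-visit text would stop these six symptoms at 20 minutes at Visit 7, and would then hold no data for measures that the SAP says will be collected. Visit 7 carries the sixth and last challenge of a series that the protocol introduction describes as building up chronicity step by step, so the gap falls at the end of the course that Part 2 is meant to observe. If staff resolved the conflict differently from one subject to the next, the late scores would be present for some subjects and absent for others for reasons unrelated to the subject.

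For the diary, the confocal subset would have an untreated record from Visit 3 but no on-treatment record from Part 1 to set beside it.

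**Working it through.** The documents state no figure on this point, so there is none to reproduce. The check is a comparison of schedules followed by a count.

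**Schedules for eyelid swelling, tearing and the four nasal, ear or palate symptoms (minutes after challenge)**

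| Visit | Procedure text (protocol 10.3.1) | Measures listed (synopsis, protocol 8.1.2 and 8.4, SAP 2.2 and 2.5) |
|---|---|---|
| 4b, 5a | 7, 15, 20 | 7, 15, 20 |
| 5b, 6a, 6b | 7, 15, 20, 25, 30 | 7, 15, 20, 25, 30 |
| 7 | 7, 15, 20 | 7, 15, 20, 25, 30 |

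Only the Visit 7 row disagrees. Its procedure times are those of Visits 4b and 5a, so carried-over wording is a plausible cause, though that is an inference. The sentence is complete in the public copy, so the gap is not a redaction.

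**Count of late cells**

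- Items: tearing, eyelid swelling, rhinorrhea, nasal pruritus, ear or palate pruritus, nasal congestion = 6.
- Planned late cells: 6 items × 2 times (25, 30) × 4 visits (5b, 6a, 6b, 7) = 48.
- Not scheduled by the Visit 7 procedure: 6 × 2 × 1 = 12.
- Share: 12/48 = 25%.

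**Other denominators, per item**

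- Late cells at Visit 7 alone: 2/2 = 100%.
- All Visit 7 cells: 2/5 = 40%.
- All cells at Visits 5b to 7: 2/(4 × 5) = 2/20 = 10%.
- All post-dose cells: 2/(2 × 3 + 4 × 5) = 2/26 = 7.7%.

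**In scores**, counting one score per item, time and subject, with the enrolment and completion figures of protocol 7.1:

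- 112 completers: 12 × 112 = 1,344 of 48 × 112 = 5,376.
- 120 enrolled: 12 × 120 = 1,440 of 48 × 120 = 5,760.

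**Diary.** Listed at Visits 3, 4b, 5b and 6b. Dispensing steps appear at Visits 3, 5b and 6b, and collection steps at Visits 4a, 6a and 7. The Visit 4b diary has neither. It concerns the confocal subset of about 36 subjects.

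**The case against.** Several points on the other side have force.

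- **The visit text may not be the only instruction.** Protocol 10.4.1 sends the reader to Appendix 1 for the schedule, and the Visit 7 sentence itself cites Appendix 2. Neither can be read in the public copy, and either might carry the missing times. A reader might infer that the late Visit 7 scores will certainly never be collected; the documents do not support that. The loss is conditional on sites following 10.3.1.10. The need to reconcile is not conditional: whatever the appendices say, 10.3.1.10 still conflicts with 8.4 and the SAP.
- **Only exploratory measures are touched.** The primary endpoints are itching and conjunctival redness at Visits 4b and 5a. The secondary scores for these six symptoms at 7, 15 and 20 minutes are scheduled at Visit 7 as planned. This stands in full.
- **The SAP promises little analysis.** SAP 16 commits to listing and summarising only a selection of exploratory measures, and no table title in SAP 20 names a 25- or 30-minute analysis. Visit 3 scores these symptoms only to 20 minutes, while SAP 8.3 defines baseline by matching time point for the primary variables and similarly for the secondary ones. The late scores therefore have no time-matched baseline at any visit, and the baseline-adjusted ANCOVA could not be applied to them as specified. A reader might infer that a planned endpoint analysis fails; at most, descriptive summaries lose their Visit 7 entries.
- **The diary is a minor item.** SAP 16.2 provides subject listings only for diary data.

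These points limit the consequence. They do not remove the contradiction, and a restriction on what is reported does not cancel the statement in SAP 16 that the measures will be collected.

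**Conclusion.** The inconsistency is real and is evident from the text: 10.3.1.10 omits two time points that the synopsis, protocol 8.4 and SAP 2.5 and 16 require at Visit 7 and that the three preceding visits schedule. No passage gives a reason for stopping these scores early at Visit 7.

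Its size is 25% of the planned 25- and 30-minute scores for these six symptoms over Visits 5b to 7, on the assumption that sites follow the visit procedure and that the unreadable appendices do not override it. That fraction should always carry its denominator. A reader might take it as a quarter of all data on these symptoms, but over all post-dose cells the share is 7.7%.

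Nor is the Visit 7 record empty: these symptoms keep their course from 7 to 20 minutes, and itching, redness and chemosis run to 30 minutes. No efficacy conclusion of the trial depends on the missing cells. The point merits correction because the loss would be permanent and is easy to prevent. The Visit 4b diary gap has the same character and a smaller reach.

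**What to change.** Reconcile the passages in one of two ways.

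1. Preferred: add 25 and 30 minutes for eyelid swelling, tearing and the nasal, ear or palate symptoms to the Visit 7 procedure in protocol 10.3.1.10, matching Visits 5b to 6b.
2. Otherwise: delete Visit 7 from these late measures in the synopsis, protocol 8.4, SAP 2.5 and SAP 16. All four places must change, or a new contradiction is left behind.

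For the diary, either add dispensing to the Visit 4b procedure and collection to the Visit 5a procedure, or remove the Visit 4b diary from the synopsis, protocol 8.4 and SAP 2.5.

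In both cases check Appendices 1 and 2 and the case report form against the chosen text.

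The cost is mainly protocol or SAP wording. The first option adds two short sets of subject ratings at minutes when the subject is already rating itching and the investigator is already grading redness and chemosis. Keeping the Visit 4b diary means one more diary for about 36 subjects. Neither change alters the sample size, the primary analysis or the length of the challenge session.

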10.4 SCHEDULE OF VISITS, MEASUREMENTS AND DOSING

10.4.1 Scheduled Visits

Refer to Appendix 1 for a schedule of visits and measurements.

If a subject is discontinued at a scheduled study visit, the remaining assessments should be captured on the Unscheduled Visit/ Early Exit Visit pages of the source document and corresponding eCRF.

10.4.2 Unscheduled Visits

For Unscheduled Visits, the reason for the visit should be clearly documented on the appropriate eCRF, including findings from all evaluations that are completed.

These visits may be performed to ensure subject safety. All information gathered at unscheduled visits should be recorded on the Unscheduled Visit/ Early Exit Visit pages of the Source Document and corresponding eCRF.

Evaluations that may be conducted at an Unscheduled Visit (as appropriate, depending on the reason for the visit), include:

- Update of Medical/Medication History
- Assessment of AEs
- Visual Acuity Using an ETDRS chart
- Pregnancy Testing
- Slit Lamp Examination
- Digital Imaging
- IOP Measurement
- Dilated Ophthalmoscopy Examination

10.5 COMPLIANCE WITH PROTOCOL

Site staff will review concomitant medication use at each visit.

If at any point during treatment the subject is experiencing discomfort or an undesirable reaction due to PRT-2761, PV, Patanol®, or Pred forte®, drug should be discontinued and the subject will exit the study.

Subjects who are inappropriately enrolled will be discontinued from the study. The reason for such discontinuation will be recorded as “protocol violation” in the source document and on the appropriate page in the CRF.

10.6 SUBJECT DISPOSITION

10.6.1 Completed Subjects

A completed subject is one who has not been discontinued from the study.

10.6.2 Discontinued Subjects

Subjects may be discontinued prior to their completion of the study due to:

- AEs

- protocol violations
- administrative reasons (eg, inability to continue, lost to follow up)
- manifest clinically active signs and symptoms of allergic conjunctivitis during the ocular and nasal allergic signs and symptoms assessment at Visit 5a [REDACTED]
[REDACTED]
- sponsor termination of study
- other

Note: In addition, any subject may be discontinued for any sound medical reason.

Notification of a subject discontinuation and the reason for discontinuation will be made to Ora and will be clearly documented on the eCRF.

10.7 STUDY TERMINATION

The study may be stopped at any time by the investigator and/or Ora with appropriate notification.

10.8 STUDY DURATION

10 office visits over a period of up to 9 weeks.

10.9 MONITORING AND QUALITY ASSURANCE

During the course of the study an Ora monitor, or designee, will make routine site visits to review protocol compliance, assess study drug accountability, and ensure the study is being conducted according to the pertinent regulatory requirements. The review of the subjects' medical records will be performed in a manner that adequately maintains subject confidentiality. Further details of the study monitoring will be outlined in a monitoring plan.

Regulatory authorities of domestic and foreign agencies, Ora quality assurance and or its designees may carry out on-site inspections and/or audits which may include source data checks. Therefore direct access to the original source data will be required for inspections and/or audits. All inspections and audits will be carried out giving consideration to data protection as well as subject confidentiality to the extent that local, state, and federal laws apply.

11 ADVERSE EVENTS

An AE is defined as any untoward medical occurrence associated with the use of an investigational product (IP) in humans, whether or not considered IP-related. An AE can be any unfavorable and unintended sign (eg, an abnormal laboratory finding), symptom, or disease temporally associated with the use of an IP, without any judgment about

causality. An AE can arise from any use of the IP (eg, off-label use, use in combination with another drug or medical device) and from any route of administration, formulation, or dose, including an overdose. An AE can arise from any delivery, implantation, or use of a medical device, including medical device failure, subject characteristics that may impact medical device performance (eg, anatomical limitations), and therapeutic parameters (eg, energy applied, sizing, dose release) associated with medical device.

All AEs spontaneously reported by the subject and/or in response to an open question from study personnel or revealed by observation, physical examination or other diagnostic procedures will be recorded in the source document and on the appropriate pages of the CRF. Any clinically relevant deterioration in clinical finding is considered an AE and must be recorded. When possible, signs and symptoms indicating a common underlying pathology should be noted as 1 comprehensive event.

Collection of AEs/SAEs will begin at the time of informed consent.

Documentation regarding the AE should be made as to the nature, date of onset, end date, severity, relationship to IP, action(s) taken, seriousness, and outcome of any sign or symptom observed by the physician or reported by the subject upon indirect questioning.

11.1 SEVERITY

Severity of an AE is defined as a qualitative assessment of the degree of intensity of an AE as determined by the investigator or reported to him/her by the subject. The assessment of severity is made irrespective of relationship to IP or seriousness of the event and should be evaluated according to the following scale:

- *Mild*: Event is noticeable to the subject, but is easily tolerated and does not interfere with the subject's daily activities.
- *Moderate*: Event is bothersome, possibly requiring additional therapy, and may interfere with the subject's daily activities.
- *Severe*: Event is intolerable, necessitates additional therapy or alteration of therapy, and interferes with the subject's daily activities.

11.2 RELATIONSHIP TO INVESTIGATIONAL PRODUCT

The relationship of each AE to the IP should be determined by the investigator using these explanations:

- ***Suspected***: A reasonable possibility exists that the IP caused the AE. A suspected AE can be further defined as:
 - *Definite*: Relationship exists when the AE follows a reasonable sequence from the time of IP administration, follows a known response pattern of the drug

class, is confirmed by improvement on stopping the IP and no other reasonable cause exists.

- *Probable*: Relationship exists when the AE follows a reasonable sequence from the time of IP administration, follows a known response pattern of the drug class, is confirmed by improvement on stopping the IP and the suspect IP is the most likely of all causes.
- *Possible*: Relationship exists when the AE follows a reasonable sequence from the time of administration, but could also have been produced by the subject's clinical state or by other drugs administered to the subject.
- **Not Suspected**: A reasonable possibility does not exist that the IP caused the AE. A not suspected AE can further be defined as:
 - *Not Related*: Concurrent illness, concurrent medication, or other known cause is clearly responsible for the AE, the administration of the IP and the occurrence of the AE are not reasonably related in time, OR exposure to IP has not occurred.

Types of evidence that would suggest a causal relationship between the IP and the AE include: a single occurrence of an event that is uncommon and known to be strongly associated with IP exposure (eg, angioedema, hepatic injury, Stevens-Johnson Syndrome); one or more occurrences of an event that is not commonly associated with IP exposure, but is otherwise uncommon in the population exposed to the IP (eg, tendon rupture); an aggregate analysis of specific events observed in a clinical trial (such as known consequences of the underlying disease or condition under investigation or other events that commonly occur in the study population independent of drug therapy) that indicates those events occur more frequently in the IP-treatment group than in a concurrent or historical control group.

